18.0 Provisions to Monitor the Data to Ensure the Safety of Subjects*

18.1 A data safety and monitoring plan has been developed for this clinical trial.

Purpose. The purpose of our data safety and monitoring plan (**DSMP**) is to safeguard the welfare of human subjects participating in the clinical trial through the regular review of safety data related to the intervention. The DSMP ensures that the research staff and principal investigator (**PI**) follow specific guidelines with respect to accurate data management and the assessment and timely reporting of adverse events associated with the investigational study Nursing Touch and Biobehavioral Stress Responses of Very Preterm Infants. The DSMP for the proposed study incorporates the Policies on Data and Safety Monitoring specified by OSU, NCH, the IRB, the Office of Regulatory Knowledge and Support in the Center for Clinical and Translational Science, and the OSU CON Data Safety Monitoring Committee (**DSMC**).

Data Safety Monitoring Committee. The DSMC is comprised of tenured faculty from the OSU CON with expertise in the conduct and analysis of clinical trials in the acute care setting. Members of the DSMC include [name] [name], Distinguished Professor of Critical Care Research and Associate Dean of Research and Innovation; and [name], Research Associate Professor and biostatistician.

Members of the DSMC have no apparent conflicts of interest related to the proposed study and are not current collaborators of any study investigators. DSMC members will report arising conflicts of interest to fellow members and the study investigators. DSMC members who develop significant conflicts of interest will resign from the DSMC.

DSMC members who leave OSU or resign their position prior to the conclusion of the clinical trial will be replaced with a new member appointed by the study investigators.

Interim Monitoring Procedures. On a monthly basis, the PI will produce interim reports specifically focusing on missing data and entry errors. The progress of the study will be monitored biannually by the college DSMC. On a biannual basis, the PI will prepare a written report on the progress of the study that will include data on: enrollment, comparison of target to actual enrollment, information on race, ethnicity, sex, overall status of the study participants, protocol deviations, and adverse or serious adverse events. These data will be collected in a spreadsheet format and reviewed by [name] (Study PI). All reports will be reviewed by the DSMC on a biannual basis. After each report is reviewed, the Committee will recommend whether the study should continue, continue with modifications, or be terminated. PI reports and minutes from DSMC meetings will also be sent to the Office of Responsible Research Practices. Co-I [name], who has extensive

experience with DSMCs and the conduct of clinical trials, will assist the PI in developing these reports.

Procedures for Adverse Events

Identification of adverse events. Study staff will be at the bedside during infant data collection and will record the occurrence of adverse events in real time. Adverse events (AEs) will be reported immediately to the PI. Adverse events may also be identified by parents or neonatal intensive care unit staff, who are encouraged to alert the PI of these events. During the consent process, participating nurses and parents of participating infants will be informed of the minimal risk nature of this study and encouraged to report any AEs immediately to study staff. The PI will maintain an electronic record of AEs and will include a description of AEs in the written report submitted biannually to the DSMC. Given the short-term duration of infant participation in the study, AEs will be tracked from the time that infant participation begins following the attachment of sensors for data collection and will continue until the end of the recovery period (i.e. 30 minutes after the final direct touch of the care episode).

Definitions. **Adverse Event:** Any unfavorable and unintended sign, regardless of whether it is considered related to the intervention; also an “unanticipated problem” of any nature (e.g., psychological or social harm; designated as unrelated, definitely related, probably related, or possible related; see below). **Serious adverse event (SAE):** Any adverse event that is fatal or life threatening, is permanently disabling or requires prolongation of hospitalization. **Life-threatening event:** Any adverse event in which the subject is at immediate risk of death from the reaction as it occurs; does not include a reaction that, if it were to occur in a more serious form, might cause death. **Unexpected event:** Any adverse event that is not identified in nature, severity, or frequency in the study protocol or consent or the event was more serious than anticipated. **Definitely Related:** An adverse event that has a timely relationship to the administration of the investigational study procedure and follows a known pattern of response for which no alternative cause is present. **Probably Related:** An adverse event that has a timely relationship to the administration of the investigational study procedure and follows a known pattern of response, but for which a potential alternative cause may be present. **Possibly Related:** An adverse event that has a timely relationship to the administration of the investigational study procedure and follows no known pattern of response, but a potential alternative cause does not exist. **Unrelated:** An adverse event for which there is evidence that it is definitely related to a cause other than the investigational study procedure; in general no timely relationship to the administration of the procedure exists, or if so, the event does not follow a pattern of response and an alternative cause is present.

Grading scale for adverse event severity. **Mild:** Transient bradycardia (defined by clinical parameters established for each patient, usually heart rate <100 beats per minute), apnea, or oxygen desaturation requiring no intervention or an increase in supplemental oxygen. Bradycardia and oxygen desaturation are defined by clinical parameters established for each patient, usually heart rate <100 beats per minute or oxygen saturation <85% lasting 10 seconds. Erythema resulting from monitoring electrodes. **Moderate:** Bradycardia, apnea, or oxygen desaturation requiring an

increase in respiratory support (i.e. hand-bagging). Epidermal stripping (i.e. non-intact skin) resulting from monitoring electrodes. Severe: Physiologic decompensation requiring intubation or cardiopulmonary resuscitation.

Review of adverse events. The study investigators will provide an initial review of all AEs to the DSMC to determine their relatedness to the research and preliminary grading of severity. For each AE, the PI will record the onset, duration, intensity, treatment required, outcome and action taken. SAEs are not expected to occur during this study. Possibly, probably, or definitely related AEs, as determined by the study team, will be reported within 24 hours to the DSMC chair for further review. The DSMC will make the final determination on AE severity and relatedness.

Reporting of adverse events. Final evaluation of relatedness and severity of AEs will be determined by the DSMC. In accordance with NCH IRB Adverse Event Reporting Policy, an AE is reportable to the IRB within 5 business days if it meets all of the following criteria: (1) the event is unexpected, (2) the event is related or probably related to study participation, and (3) is serious and/or suggests that the research places subjects or others at a greater risk of physical or psychological harm than was previously known or recognized. Additionally, per NCH IRB policy, all protocol deviations or violations that harmed participants or indicate that others might be at increased risk of harm, breaches of confidentiality, and new literature that may affect willingness to participate are reportable events within 5 business days. AEs that must be reported annually with continuing review include: (1) minor protocol deviations that do not indicate an increased risk of harm, and (2) AEs that are not serious or unexpected. After review by the DSMC, all reportable AEs will be submitted by the PI to the NCH IRB. Reportable AEs will be forwarded to the NIH/NINR Program Officer by the NCH IRB. In addition, reportable AEs and the IRB acknowledgement letter and cumulative reportable AEs, SAEs, and unanticipated problems will be forwarded to the NIH/NINR Program Officer with the PI's Annual Progress Report. .

Assessment of External Factors. Because essential nursing care involves the handling of preterm infants, we do not expect 2.5 minutes of comforting touch provided during the care episode to increase the risk for AEs beyond what is expected during essential nursing care. The study investigators will meet monthly to discuss new developments and safety concerns. Prior to each monthly meeting, the PI will conduct a literature search to identify new developments that might affect the evaluation of risk for this study.

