6.2 **Procedures. Aims 1.** Infants will be enrolled during the first 10 days of life. We will collect demographic and clinical data from the infant's electronic health record (**EHR**) after enrollment and throughout the hospitalization. Because stress responses may differ based on postnatal age⁸¹, data collection for stress responses will occur between 10 and 20 days of life. To eliminate variance in cortisol due to diurnal patterns, we will perform all observations at the same time of day for all infants, between 1000 and 1300. Observations will occur on two consecutive days unless infants are not available due to off-unit or other scheduled procedures. In this case, the second observation will occur on the next day that the infant is available. Infants will be assigned to receive standard care or standard care with a NaTI in a randomly assigned sequence. For the two observed care episodes, we will require that nurses provide this care exclusively to limit confounding by the participation of additional caregivers. With assistance from the bedside nurse, the researcher, who is a Registered Nurse, will attach monitoring electrodes for vital signs, HRV, and SCRs during the care episode prior to the observed care to minimize stress responses from handling and monitoring prior to the baseline period (Fig 2). Nurses commonly attach monitoring electrodes as part of their clinical practice.

[figure not shown]

Figure 2. Timeline of study measures.

Measures, Aims 1:

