9.0 Study Timelines*

9.1 Participation for infants each day will last approximately 6 hours and will begin when electrodes to measure SCRs are attached to the infant during the care episode prior to the observed care. Infant participation to measure biobehavioral responses to care will last approximately 24-48 hours and will include two 6-hour observation periods as described above, one each on two consecutive days. If a participating infant is not available on the second consecutive day due to an off-unit or scheduled procedure, data collection will resume on the next possible day. Total infant participation in the study will last between 5-7 weeks, depending on PMA at birth and the timing of the neurobehavioral assessment planned for 35 weeks PMA. Nurse participation is expected to last 15-20 minutes or the time required to complete the demographic questionnaire and study questionnaires. Nurses may be asked to complete additional sets of questionnaires if they provide the NaTI more than once.

We expect that infant enrollment will require four months. Nurse participants will be enrolled at the time of infant data collection for infants.

Preliminary data analysis should be complete 9 months after enrollment of the first infant participant.

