11.1 **Infant participants.** Participants in this study will be preterm infants born 27-30 weeks PMA. We will not enroll extremely preterm infants of uncertain viability. The study procedures pose no more than minimal risk to infant participants and may have potential, if slight, benefit for infants. We will obtain written informed consent from parents prior to the initiation of any study procedures. Parents will be given adequate time to consider participation in the study prior to providing written informed consent. Infant participants will not provide assent, as infants are developmentally unable to do so.

Nurse participants. Nurse participants may include pregnant women. This is a minimal risk study for nurse participants and poses no physical risk to a pregnant nurse's fetus. Nurse participants will provide written informed consent prior to participation.

12.0 **Local Number of Subjects**

12.1 **Infant participants.** All infants will be enrolled from the NCH NICUs. We will enroll up to 20 infants to collect complete, usable data from 16 infants.

Nurse participants. Nurses will be those employed in the NCH NICUs. We will invite all nurses who provide care to infants receiving the NaTI to participate in the survey study, providing up to 20 total opportunities for nurse responses. Assuming 80% participation, we expect up to 16 nurse responses.

13.0 **Recruitment Methods**

13.1 **Infant participants.** After identifying an eligible infant, study staff will meet with parents in the NICU or in the mother's postpartum hospital room to introduce the study. Study staff will wait until parents have visited the NICU to see their infant and receive a medical update prior to attempting to contact parents. Study staff will check with bedside caregivers in the NICU or the postpartum unit to ensure that it is an appropriate time to meet with parents. During the first meeting, study staff will provide parents with an informational flier that outlines the study purpose and procedures. We will ask parents if it is a good time to discuss their infant's eligibility for a research study and will conduct any follow-up discussion either in person or over the phone based on parental preference. Study staff will provide a thorough overview of the study, including the study purpose, procedures, potential

PROTOCOL TITLE: Pilot Study of Nurse-Administered Touch and Biobehavioral Stress Responses of Preterm Infants (Pilot NAT-BIO Study)

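### On the stated schedule, the DSMC's first continue, modify or terminate recommendation can come after every infant has received the NaTI

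*Combined protocol and SAP*

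**What the plan says.** Section 18.1 gives the monitoring plan's purpose as to "safeguard the welfare of human subjects participating in the clinical trial through the regular review of safety data". On frequency it says "The progress of the study will be monitored biannually by the college DSMC", and on the outcome of each review: "After each report is reviewed, the Committee will recommend whether the study should continue, continue with modifications, or be terminated". Once a month, "the PI will produce interim reports specifically focusing on missing data and entry errors".

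The trial's pace is set elsewhere. Section 9.1: "We expect that infant enrollment will require four months". Section 12.1: "We will enroll up to 20 infants to collect complete, usable data from 16 infants". Section 6.2: "Infants will be enrolled during the first 10 days of life", and "data collection for stress responses will occur between 10 and 20 days of life". Each infant is observed on two days, normally consecutive, and receives the NaTI on one of them.

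Section 18.1 also provides other safety routes:

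- Adverse events are recorded at the bedside and go to the PI at once.
- The investigators give the DSMC an initial review of all adverse events, with no timing stated.
- Events the study team judges possibly, probably or definitely related go to the DSMC chair within 24 hours.
- The DSMC has the final say on severity and relatedness.
- The investigators meet monthly on safety.

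Sections 4.2 and 6.3 give per-infant criteria for stopping the NaTI within a care episode.

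**The concern.** The interval between committee reviews is longer than the period in which infants are treated. A recommendation on whether the study should go on protects participants only if some remain to be treated. The plan fixes no date for the first review and ties none to the number of infants treated.

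Cumulative counts matter here because single events say little. Section 15.1 already names bradycardia, apnea and desaturation as possible, and they also occur with ordinary care. A modest excess under the NaTI would show mainly when the two conditions are compared across infants. The list of contents for the biannual report includes adverse events but does not ask for them by condition.

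**Working it through.** **Inputs.** Enrolment 4 months (9.1). Up to 20 infants (12.1). Enrolment by day 10 and observation between days 10 and 20 of life (6.2), so the lag from enrolment to NaTI is at most 20 days. DSMC review twice a year, read as every 6 months (18.1). One month = 365.25/12 = 30.44 days. The start of the six-month clock is not stated, so both cases are worked.

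**1. The four months.** The plan gives no derivation, so this is a plausibility check. Section 25.1 reports 73 infants of similar gestation enrolled for a study run from October 2017 to December 2018, which is 13 to 15 months depending on the exact dates. The rate is 73/15 = 4.9 to 73/13 = 5.6 per month. Twenty infants would then take 3.6 to 4.1 months, in line with the stated four.

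**2. Last exposure.** 4 × 30.44 = 121.8 days with no lag. With the longest lag, 121.8 + 20 = 141.8 days, or 141.8/30.44 = 4.66 months.

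**3. Clock from first enrolment.** The first review is at 6 × 30.44 = 182.6 days. The margin is 182.6 − 141.8 = 41 days (longest lag) to 182.6 − 121.8 = 61 days (no lag). No infant remains to be treated. A second review would fall at month 12, after the preliminary analysis that 9.1 expects by month 9.

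**4. If enrolment slips.** Some infants remain untreated at month 6 only if enrolment exceeds (182.6 − 20)/30.44 = 5.3 months with the longest lag, or 6 months with none. With steady accrual and the longest lag, the number treated by month 6 is 20 × (6 − 20/30.44)/L for enrolment length L. That is about 18 of 20 at L = 6 and about 12 of 20 at L = 9.

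**5. Fixed committee calendar.** Meetings 6 months apart cannot both fall in a window of at most 4.66 months, so at most one does. If the calendar is unrelated to the trial's start (an assumption), the chance that one falls inside is 4/6 = 67% to 4.66/6 = 78%. At 20/4 = 5 infants a month, a meeting at month 2 would come after 5 × (2 − 0.66) = 7 to 10 infants, and at month 3 after 5 × (3 − 0.66) = 12 to 15.

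**6. The other routes.** Each is compared with what is needed: a timed, cumulative look by the independent committee that can lead to a recommendation.

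- 24-hour report: timed and reaches the chair, but covers single events, depends on the study team's own relatedness call, and is described only as leading to a determination of severity and relatedness.
- Initial review of all adverse events: reaches the committee, but has no timing. The stated vehicle for describing them is the biannual report.
- Monthly investigator meeting: timed, but not the committee.
- Monthly PI report: focused on missing data and entry errors.
- Per-infant stopping: applies to one care episode, not to the study.

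**The case against.** A good part of the case on the other side stands. The plan never starts the clock at first enrolment. A college committee may keep its own calendar, and on the random-calendar assumption a review during treatment is more likely than not. Four months is an expectation, not a cap. The intervention is 2.5 minutes of static touch, given in the same manner as touch nurses already provide at their discretion, and the protocol calls the study minimal risk. Institutional policies that 18.1 incorporates, and that are not in these documents, may set the frequency.

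Two stronger readings are tempting. A reader might infer that the committee cannot act on any infant, so the safeguard does not operate at all. The documents do not support that: the clock start is open, a calendar meeting could fall inside the window, and related events reach the chair within a day.

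A reader might also infer that an excess of bradycardia or desaturation would be labelled unrelated and go unseen. The definitions in 18.1 weigh against this. An event timely to the procedure and following a known pattern is probably related even if another cause may be present, while unrelated requires evidence of a definite other cause. The committee also makes the final determination.

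What does not stand is that these provisions close the gap. None sets a time during treatment at which the committee sees cumulative data and decides about the study.

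**Conclusion.** The point holds as a gap in the timing of oversight. If the clock starts at first enrolment and enrolment takes the expected four months, all of up to 20 infants are treated by about month 4.7, some 6 to 9 weeks before the first scheduled recommendation. On a fixed calendar at most one review falls within treatment, at a point nobody has chosen. The result rests on reading the stated frequency as every six months and on enrolment not running past about 5.3 months.

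Nothing here is evidence that the NaTI causes harm. Given the minimal-risk setting and the partial routes already in place, this is a cheap improvement rather than a flaw that puts the trial in doubt.

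**What to change.** In 18.1:

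- Add at least one DSMC review tied to accrual, for example when about half the infants, or another fixed number, have completed both observation days. Keep biannual review as a minimum in case enrolment runs longer.
- Tabulate adverse events by condition. List NaTI stops as a count for NaTI episodes only, because standard care has no comparable event.
- Have these tables prepared by someone other than the outcome assessors and analysts whom Section 3.1 promises to blind.
- State that a 24-hour report to the chair may prompt a recommendation on the study, and say how soon the committee responds once the accrual trigger is reached.

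At 5 infants a month the tenth infant is enrolled at month 2 and completes by month 2.66 at the latest. Then 20 − 5 × 2.66 = about 7 infants, and up to 10 with no lag, are still to be enrolled. Each week of turnaround uses about 5 × 7/30.44 = 1.15 of them.

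The cost is one or two short reports from a spreadsheet already kept, plus naming a preparer. The limit is that early looks at few infants detect only gross problems. With 5 infants, even 5 of 5 differing in the same direction gives a two-sided exact p of 2 × 0.5^5 = 0.0625. With 10 infants and no events of a given kind, the one-sided 95% upper bound on its frequency is still 1 − 0.05^(1/10) = 26%.
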